8.1. General statistical methods

Summary statistics will be presented for both the treatment and control groups. Continuous variables will be summarized by the number of observations, mean, standard deviation, median, minimum, and maximum. Categorical variables will be summarized using frequency counts and percentages. Descriptive analyses of the distributions of the e-cigarette seller behavior outcomes between two types of attire (treatment and control groups), including successful purchases, inquiring about buyer age, requesting ID cards for age verification, and dissuading buyers from use, as well as store environment features, and sellers' demographic characteristics, will be conducted with t-tests and chi-square tests detecting statistically significant differences.

The significance level for comparisons between the two groups is set at $\alpha=0.05$ (two-sided). Differences between the study groups will be considered statistically significant if the p-value is less than 0.05. All analyses will be performed using Stata MP 17.

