- Mobile phone store-----primarily sells mobile phone cases, data cables, and screen protectors.

Others (such as: large supermarkets, clothing stores) _____ (i.e. next to the entrance of large supermarkets)

None of the above

10. In which of the following ways does the exterior decoration of the store attract the attention of passers-by? [Multiple choice questions] *----Brand names or store names such as "RELX" do not count as advertising.

General print advertising (posters, banners, flyers, etc.)

Backlit or illuminated advertising----refers to advertising that features LED lighting, video, and short clips accompanied by dynamic or static text display. [Note: When not illuminated, it is considered standard printed advertising.]

Three-dimensional advertising, such as large fixtures — refers to large e-cigarette installations used in e-cigarette stores for product promotion or promotional activity displays, including large props, dolls, etc. (see the figure below).

Other _____

No advertising

11. Area of large billboards: [Fill in the blanks _____] *---- Note: Take the prescribed poster as the first figure below. There may be more than just e-cigarettes in the advertisements in the second figure below. If there are too many advertisements in the third figure below, fill in 10. [For Question #10 above, if "Others" or "No advertising" is chosen, please fill in 0 for Question #11.]

12. Are there any billboards with the following characteristics outside e-cigarette stores?

[Multiple choice questions] *

Use of celebrity endorsements

Scenic photos, such as mountains, rivers, trees, and blue sky

Contains images of cartoon characters or animals ---- on billboards

□ Price discounts or promotional activities----advertisements for price discounts or promotions often include phrases such as 'limited-time offer,' 'X% off,' 'price reduction,' 'buy and get xxx free,' 'grab a bargain,' or 'carnival season.' and so on.

□ Ads showing e-cigarette flavors, such as photos of fruit

□ Other _____

Depends on options 1, 2, 3, or 4 of Question #10.

13. From the perspective of pedestrians, is there a recognizable "No Use by Minors" sign [Single Choice Question] *----The following large warning signs or clearly visible signs that can be seen from the outside

Yes

No

In-store communication and records 1

14. Can you enter the store to observe and record? Please select one of the following [Single Choice Question] *

Yes

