## 2.3. Statistical Methods

### 2.3.1. General Considerations

Summary statistics will be presented for both the treatment and control groups. Continuous variables will be summarized by the number of observations, mean, standard deviation, median, minimum, and maximum. Categorical variables will be summarized using frequency counts and percentages. Descriptive analyses of the distributions of the e-cigarette seller behavior outcomes between two types of attire (treatment and control groups), including successful purchases, inquiring about buyer age, requesting ID cards for age verification, and dissuading buyers from use, as well as store environment features, and sellers' demographic characteristics, will be conducted with t-tests and chi-square tests detecting statistically significant differences.

The significance level for comparisons between the two groups is set at  $\alpha=0.05$  (two-sided). Differences between the study groups will be considered statistically significant if the p-value is less than 0.05. All analyses will be performed using Stata MP 17.

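### Billboard area (Question 11) mixes measured values with instructed codes of 0 and 10, so its mean, SD and maximum would not describe true area if it is summarised as a continuous variable

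*Protocol*

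**What the plan says.** The form is in Protocol Appendix 4, under the outside-store observation.

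- **Question 10** asks how the exterior attracts attention. It is marked multiple choice. Its options are, in order, print, illuminated, three-dimensional, 'Other' and 'No advertising'.
- **Question 11** asks for the area of large billboards as a fill-in value. Its note carries two coding instructions. The first is "If there are too many advertisements in the third figure below, fill in 10". The second says that if 'Others' or 'No advertising' in Question 10 "is chosen, please fill in 0 for Question #11".
- **Question 12** asks which features the billboards have, and its routing reads "Depends on options 1, 2, 3, or 4 of Question #10". Option 4 is 'Other'.

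On analysis, SAP 2.3.1 says "Continuous variables will be summarized by the number of observations, mean, standard deviation, median, minimum, and maximum", and Protocol 8.1 has the same rule. Both sections say that comparisons of seller behaviours, store environment features and seller demographics between attire groups "will be conducted with t-tests and chi-square tests detecting statistically significant differences". SAP 2.2.2 lists advertising among the store covariates without giving a scale. Documenting advertisements falls under the second exploratory objective (Protocol 2.4, SAP 1.2.3). Neither document says how the codes 0 and 10 are to be treated, and Protocol 8.7 on missing data does not cover them.

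**The concern.** A column that mixes measurements with instructed codes should not be averaged as if every entry were a measurement. Here 10 stands for stores with too much advertising to assess. Zero stands for two different situations: no advertising, and advertising of which at least part was classed as 'Other'. The general rule for continuous variables would turn this mixture into a mean, an SD and a maximum.

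What is at stake is the description of exterior advertising under the exploratory objective. If area were chosen to represent the advertising covariate, the measurement of one adjustment variable would be affected as well.

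**Working it through.** Neither document gives a mean, SD or maximum for billboard area, so there is no stated figure to reproduce. The check is a reading of the form against the analysis rule, followed by an illustration on assumed inputs.

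**1. Does the general rule reach Question 11?** The seller behaviours compared are yes/no items. Seller sex and age are categories, and the other store environment items are tick-box. The only other numeric store item is the lowest product price (Question 36), which is not an environment feature. Question 11 is therefore the one environment item to which the mean, SD, maximum and t-test rule can apply, although neither document names it.

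**2. Are Questions 10 to 12 consistent?**

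| Ticked in Question 10 | Question 11, read literally | Question 12 asked? |
|---|---|---|
| No advertising | 0 | No |
| 'Other' only | 0 | Yes |
| Print + 'Other' | 0 | Yes |
| Print only | measured, or 10 if too many | Yes |

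The second and third rows can hold billboard features beside a billboard area of 0. In the third row the store also has print advertising that could have been measured.

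**3. What do the codes do to the mean?** Let p be the share of stores coded 10 and T their mean true area. Let q be the share wrongly entered as 0 and Z their mean true area.

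Error in mean = p(10 − T) − qZ

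The second term can only lower the mean. The first term lowers it if T exceeds 10 and raises it if T is below 10. The instruction is triggered by too many advertisements, not by an area above 10. The reference figure is not available and no unit is visible, so the sign of the first term is unknown.

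**4. Illustration for one possible meaning of code 10.** Assumptions, none from the documents: 30% of stores have no advertising; area in the rest is lognormal with median m and log-SD s; every value above 10 is entered as 10. Write E = m·exp(s²/2). The mean of the capped area is then

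C = E·Φ[(ln(10/m) − s²)/s] + 10·{1 − Φ[ln(10/m)/s]}

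- m = 2, s = 0.8: E = 2.754 and C = 2.665. True mean 0.7 × 2.754 = 1.93; recorded 0.7 × 2.665 = 1.87.
- m = 4, s = 1.2: E = 8.218 and C = 4.948. True mean 0.7 × 8.218 = 5.75; recorded 0.7 × 4.948 = 3.46.
- If a further 15% of stores have real billboard area but are entered as 0 because of 'Other', the recorded means become 0.55 × 2.665 = 1.47 and 0.55 × 4.948 = 2.72.

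In a simulation on the same assumptions, code 10 alone moved the SD from 2.52 to 2.17 in the mild case and from 12.93 to 3.71 in the wide case, and left the median unchanged. Adding the 15% of false zeros lowered the median from 1.27 to 0.68 and from 2.03 to 0.80. Under this reading of code 10 the maximum cannot exceed 10.

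**5. Is the comparison of arms affected?** The same instructions apply in both arms, and the exterior is recorded before the buyer enters (Protocol 5.2, 7.6). With 540 independent stores per arm and the same coding in both, a two-sample t-test rejected in 5.2% of 4,000 simulated trials (clustering ignored). This is close to the nominal 5%.

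**The case against.** The strongest reply is that no plan to report area exists. Billboard area is not a primary, secondary or other outcome. The covariate entry follows three items recorded as presented or not, so presence or type of advertising from Question 10 fits it at least as well. That stands, and it makes the point conditional on Question 11 being summarised under the general rule.

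A reader might go further and infer any of the following, which the documents do not support:

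- **That area is capped at 10 and the reported mean is too low.** Nothing forbids a measured value above 10, and a cluttered store with a true area below 10 would be coded upward. The illustration above assumes a strict cap. With a smaller assumed median, such as m = 1 and s between 0.8 and 1.0, only about 0.2% to 1% of advertised areas would exceed 10.
- **That stores with 'Other' advertising would be described as having none.** Question 10 keeps the two answers apart. Because Question 11 concerns large billboards only, 0 may be correct for a store whose advertising is of another kind.
- **That the t-test is invalid or the trial result is affected.** The coding does not differ by arm, and its type I error was unaffected in the check above.

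It can also be said that 'Others' in the zero instruction means 'Others' alone. That is a possible intention, but the form does not say it, and Question 12 would still ask about billboards at a store with area 0.

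**Conclusion.** The point holds in a limited form and is minor. The two coding instructions are in the form, they conflict with the multiple-choice format of Question 10 and the routing of Question 12, and no analysis rule covers them. If Question 11 is summarised as a continuous variable, its mean, SD and maximum would not describe true area.

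False zeros can only lower the mean. The size and direction of the error from code 10 cannot be determined from the documents, and the illustrative range (almost none to roughly a 40% fall, 5.75 to 3.46) rests wholly on the assumed distribution and an assumed strict cap. The comparison of arms and the primary outcome are not biased by this coding. The harm is to one descriptive result, and to covariate measurement only if area is the scale chosen for advertising.

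**What to change.** **On the form:** limit the forced 0 to stores with no large billboard; align Questions 10 to 12 so that a store asked about billboard features can also record an area; record 10 as a flagged code meaning too many to measure; and state the unit.

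**In the SAP:** report Question 11 as three categories (none, measured, too many to measure) with counts and percentages, plus the median of the measured areas. Do not report its mean, SD or maximum. State the scale on which advertising enters the covariate list.

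**If data are already collected:** use Question 10 to flag zeros from stores that ticked 'Other', especially together with another type of advertising, and do not average them as zero. Their true area cannot be recovered from Question 10, so report how many there are.

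The cost is a few lines of form and SAP text and a slightly coarser summary of one descriptive item. The category for code 10 should not be labelled as 10 or more, because the form does not give it that meaning.

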No, the e-cigarette store is not open (please skip to the end of the questionnaire and submit your answer sheet)

No, the seller is not in the store (please skip to the end of the questionnaire and submit your answer)

No, other _____ * (please skip to the end of the questionnaire and submit your answer sheet)

15. Is the tobacco retail license visible [Single choice question] *

Yes

No

16. Is there a "No use by minors" slogan in the store (excluding slogans on product packaging) [Single-choice question] *

Yes

No

17. Are there any of the following health warning signs in the store (excluding slogans on product packaging) [Single choice question] *

Yes, there is a "Smoking is harmful to health" sign

Yes, there is a "E-cigarettes are harmful to health" sign

Yes, both of the above exist

No

18. Are there children's toys, car models, figurines, and/or other decorations placed on the shelves or counters? [Note that these decorations need to be targeted at teenagers.] [Single Choice Question] *

Yes, specifically _____ *

No

19. Gender of the seller: (When there are multiple sellers, this question refers to the seller who communicates with the simulated buyer the most. The same applies to the questions below.)

Male

Female

20. Age of the seller (the simulated buyer needs to estimate) [Single-choice question] *

18-24 years old

25-29 years old

30-39 years old

>40 years old

21. Did the seller ask the simulated buyer if he or she was an adult? [Single Choice Question] * -----Questions such as "Are you an adult?" "Are you over 18?" "How old are you?" "Are you a student?" etc.

Yes

No

22. Did the seller ask to see the simulated buyer's ID? (If the seller requires you to fill in identity information on the system, please select Yes.) [Single Choice Question] *

Yes

No

23. Did the seller ask the simulated buyer to leave? (No sales communication) [Single Choice Question] * ----- If the seller does not check the age until the simulated buyer pays, the sales communication has been completed at this point. In this case, you should select "No" and continue to fill in the questionnaire.

○No

- Yes, the seller asked you (the simulated buyer) to leave without asking about their age. (Please skip to the end of the questionnaire and submit your answer.)
- Yes, the seller asked you (the simulated buyer) to leave after asking their age. (Please skip to the end of the questionnaire and submit your answer.)

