- Yes, the seller asked you (the simulated buyer) to leave after knowing that he or she did not have an ID card. (Please skip to the end of the questionnaire and submit your answer.)

In-store communication and records 2

24. Does the e-cigarette store sell the following types of e-cigarettes and accessories
[Multiple choice questions] **

Disposable e-cigarettes ----- Disposable e-cigarettes refer to those e-cigarettes that cannot be disassembled, refilled, or changed by the user and are thrown away after use. They can also be rechargeable. For example, the seller might describe them to you as "rechargeable for 1,000 puffs."

Reloadable e-cigarettes and/or cartridges ----- Reloadable e-cigarettes usually consist of two parts: a cigarette rod and a cigarette cartridge. The cigarette rod can be recharged and reused, while the cigarette cartridge is thrown away after use.

Open e-cigarettes that the user refills with e-liquid himself or herself ----- The e-liquid tank of open e-cigarettes is open and refillable. It can be refilled 3-6 times for continued use. The atomizer has a long service life.

Auxiliary accessories for e-cigarettes, such as protective cases, lanyards, etc.

Other, _____

25. Other items sold in the e-cigarette stores: [Multiple choice questions] *

No products other than e-cigarettes are sold

Power bank rentals

Addictive substances, such as tobacco, alcohol, and betel nut

Other _____

26. Did the seller proactively dissuade the simulated buyer from trying e-cigarettes? [Single Choice Question] * ----- The seller will tell you (the simulated buyer) that e-cigarettes are harmful, addictive, impossible to quit, don't try them, etc., in an attempt to discourage you from buying them.

Yes

No

27. The most popular flavor recommended to you (the simulated buyer) by the seller is [fill in the blank] * ----- Ask the seller, "With so many varieties, what are the differences?" and then, "Which one sells better?"

28. The second most popular flavor recommended to you (the simulated buyer) by the seller is [fill in the blank] * ----- If the seller only recommended one flavor in the previous question, you can fill in "none" for this question.

29. Is there a "Free Trial" sign or disposable filters in the store [Single-choice question] * -----Pay attention to whether there are disposable filters at the cashier]

Yes

No

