30. Did the seller proactively mention the free trial? [Single-choice question] * -----The seller had a higher chance of letting you (the simulated buyer) try it, and might even assemble the e-cigarette and hand it over to you.

Yes

No

31. Are illegal flavored e-cigarettes sold? [Single Choice Question] * ----- Usually, illegal flavored e-cigarettes are not placed on display, lack obvious warning slogans on the packaging, and the product may be labeled in English.

Yes

No

32. Does the e-cigarette store sell illegal e-cigarettes with the following flavors [Multiple choice questions] *

- Fruit flavor
- Candy flavor
- Food or drink flavors
- Mint flavor
- herbal vaporizer
- Other, _____
- None of the above

Question #32 depends on option 1 of Question #31.

33. Did the seller proactively mention illegal e-cigarette products such as "milk tea cups" and "Coke cans" [Single-choice question] *

- Yes
- No

34. Does the information delivered to you (the simulated buyer) by the seller include the following? (Select in order) * ----- Use "E-cigarettes are very popular recently..." to potentially guide the seller to describe the reasons for the popularity of e-cigarettes.

- None
- E-cigarettes are less harmful

- [] E-cigarettes can be used in more places
- [] E-cigarettes are easily accepted by people around them
- [] E-cigarettes have a variety of flavors
- [] E-cigarettes do not produce unpleasant odors
- [] Other, _____

35. Are e-cigarettes promoted in the following ways? [Multiple choice questions] * -----

Ask "Are there any promotions?"

- Price discounts (including coupons, limited-time activities, group purchase discounts, etc.)
- Free products
- Small gifts
- Membership activities, points rewards
- Others _____
- None of the above

36. The lowest price of e-cigarette products is: [Fill in the blanks] * ----- If the cheapest one is a disposable e-cigarette, buy it and fill in the price. If there are only reloadable e-cigarettes in the store, you need to fill in the sum of the prices of the cartridges and the cigarette rods.

37. Did you (the simulated buyer) successfully buy e-cigarettes [single-choice question] *

- Yes
- No

38. Did the seller take the initiative to add your (the simulated buyer's) contact information?

[Single Choice Question] * ----- Pay attention to whether the seller took the initiative; you (the simulated buyer) should not take the initiative to ask. Please be sure not to agree to add WeChat.

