##### **Secondary Outcome Measures**

- The seller verbally inquiring about the simulated buyer's age
- The seller requesting ID cards from the simulated buyer for age verification
- The seller dissuading the simulated buyers from using e-cigarettes

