#### **2.3.5. Subgroup Analysis**

For matched e-cigarette and cigarette stores, we will employ McNemar's tests to assess the distinctions in the outcomes between e-cigarette stores and cigarette stores. Rates of successful e-cigarette purchases stratified by age checking behaviors and buyer attire will also be reported. Planned subgroup analyses are intended to explore potential effect modifications of gender, age, metropolitan area and store types.

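### The form's main-seller rule carries over to the age, ID, ejection and dissuasion items, so acts by a second staff member can be recorded as No and the three secondary outcomes under-counted

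*Protocol*

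**What the plan says.** Question 19 of the e-cigarette store form (Protocol Appendix 4) asks for the seller's sex. Its note covers stores with more than one seller: "this question refers to the seller who communicates with the simulated buyer the most. The same applies to the questions below". No end point is given for that instruction.

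Four later items ask about the seller in the singular:

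- Question 21: "Did the seller ask the simulated buyer if he or she was an adult"
- Question 22: "Did the seller ask to see the simulated buyer's ID"
- Question 23: whether the seller asked the buyer to leave without any sales communication. Each of its Yes options ends the form.
- Question 26: "Did the seller proactively dissuade the simulated buyer from trying e-cigarettes"

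Questions 21, 22 and 26 are the fixed items behind the three secondary outcomes. Protocol 6.2 lists those outcomes for sellers in general, with no main-seller limit. SAP 2.2.1 uses the singular, for example "The seller requesting ID cards from the simulated buyer for age verification", and has no rule for several staff. Under Protocol sections 3 and 7.1.3, stores are allocated in clusters and each receives one buyer.

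The purchase item, Question 37, names no seller: "Did you (the simulated buyer) successfully buy e-cigarettes".

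**The concern.** The rule suits Questions 19 and 20, which need one person whose sex and age can be recorded. It does not suit the behaviour items. If the person who talks to the buyer most asks nothing, but a colleague, owner or cashier asks for ID, the store has checked age. A buyer who follows the note records that it has not.

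Three things are at stake:

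- **Level.** Errors from this source run one way, so recorded rates of age inquiry, ID request and dissuasion, and the maps built on them, can only be too low. This matters because Protocol 8.6 and SAP 1.4 call describing seller behaviour nationally the primary goal.
- **Contrast.** The attire comparison on these outcomes can be distorted. Questions 21 and 22 also carry the age-verification part of the primary objective.
- **Classification.** SAP 2.3.5 (as Protocol 8.5) states: "Rates of successful e-cigarette purchases stratified by age checking behaviors and buyer attire will also be reported". A sale stopped by a colleague's ID request would be counted as no check and no sale.

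There is also a form-logic effect. A second-seller ejection answered No at Question 23 does not trigger the skip, so the buyer meets later required items that may not have been observed.

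**Working it through.** **Reach of the rule.** The note refers to questions in the plural and follows Question 19, so it extends past Question 20. Questions 21, 22, 23 and 26 come later and use the same term. Question 37 asks about the buyer's own success, so the rule does not alter its answer.

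**Size.** The documents give no figure to reproduce: neither the share of visits with several sellers, nor the share of checks made only by a second seller, nor the rate of any secondary outcome by arm. What follows is an illustration on assumed inputs:

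- true check rates of 0.60 (uniform) and 0.40 (casual), a difference of 20 points and a risk ratio of 1.50;
- *m*, the share of visits with more than one seller, equal in both arms;
- *s*, the share of true checks in those visits made only by someone other than the main seller (*s_u* uniform, *s_c* casual);
- the same true rate in single-seller and multi-seller stores.

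Recorded rate = true rate × (1 − *m* × *s*).

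With *m* = 0.3 and *s* = 0.3 in both arms:

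- uniform: 0.60 × (1 − 0.09) = 0.546
- casual: 0.40 × (1 − 0.09) = 0.364
- difference 0.182, risk ratio 1.50

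The planned logistic models estimate odds ratios, and these do shrink with equal shares: from (0.60/0.40)/(0.40/0.60) = 2.25 to (0.546/0.454)/(0.364/0.636) = 2.10.

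Range, in percent and percentage points:

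| *m* | *s_u* | *s_c* | Uniform | Casual | Difference | Risk ratio |
|---|---|---|---|---|---|---|
| 0.1 | 0.10 | 0.10 | 59.4 | 39.6 | 19.8 | 1.50 |
| 0.1 | 0.10 | 0.05 | 59.4 | 39.8 | 19.6 | 1.49 |
| 0.1 | 0.05 | 0.10 | 59.7 | 39.6 | 20.1 | 1.51 |
| 0.3 | 0.30 | 0.30 | 54.6 | 36.4 | 18.2 | 1.50 |
| 0.3 | 0.30 | 0.15 | 54.6 | 38.2 | 16.4 | 1.43 |
| 0.3 | 0.15 | 0.30 | 57.3 | 36.4 | 20.9 | 1.57 |
| 0.5 | 0.50 | 0.50 | 45.0 | 30.0 | 15.0 | 1.50 |
| 0.5 | 0.50 | 0.25 | 45.0 | 35.0 | 10.0 | 1.29 |
| 0.5 | 0.25 | 0.50 | 52.5 | 30.0 | 22.5 | 1.75 |

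**Direction.** The recorded difference is 0.20 − *m*(0.60 *s_u* − 0.40 *s_c*). It shrinks when *s_c* is below 1.5 × *s_u*, is unchanged at equality, and grows above it. The risk ratio moves only if *s_u* and *s_c* differ. Both recorded rates fall whenever *m* and the relevant *s* are above zero.

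**The case against.** The strongest case on the other side has four parts.

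1. **The literal reading may not be what buyers did.** The note sits in brackets under the item on seller sex. A colleague who steps in to demand ID or eject the buyer may become the person who communicates most. The script in Protocol Appendix 2 asks about age and ID checks without a main-seller limit. Protocol 7.4.1 promises a manual explaining the items, which is not reproduced, and 7.4.2 requires field practice until more than 90% of objective items are correct. This stands as a limit on certainty. It does not supply a stated rule for counting a second seller's act, so two buyers could code the same event differently.

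2. **Tying behaviour to one person is coherent.** SAP 2.2.2 adjusts for the seller's sex and perceived age, and SAP 2.2.1 is worded in the singular. That justifies keeping the rule for the covariates. It does not make a check by another staff member any less a check by the store.

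3. **Several sellers may be uncommon.** The form treats this as a special case, and Question 14 has an option for the seller being absent, which suggests one seller is usual. With *m* and *s* at 0.1, the distortion is at most 0.4 points in the table.

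4. **The effect on the attire contrast is not known.** A reader might infer that second-seller interventions are likelier under the uniform and so pull the contrast toward no effect. The documents do not show this. More checks in the uniform arm is not enough: the share made only by a second seller has to differ. Protocol 1.2 says uniforms make school-aged buyers easier to identify, which could equally mean that the main seller acts first. This objection stands.

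**Conclusion.** The form, as written, is narrower than the outcomes it feeds. Followed literally, it under-records all three secondary outcomes in stores with several sellers, can misplace visits in the stratified purchase rates, and can fail to trigger the skip at Question 23.

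The size cannot be established from the documents. On the middle assumptions with equal shares, a true 20-point difference is recorded as 18.2 points and the risk ratio is unchanged. A casual share half the uniform share gives 16.4 points, and the reverse gives 20.9. No one direction of bias in the attire contrast can be claimed.

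A reader might also infer that the primary result is at risk. It is not from this source, because Question 37 does not depend on which seller acted. The point is minor to moderate and concerns the secondary outcomes, including the age-verification part of the primary objective.

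**What to change.** **Before fieldwork:**

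- Limit the main-seller note to Questions 19 and 20. Seller sex and age stay as covariates describing the main seller.
- Reword Questions 21, 22, 23 and 26 to ask whether any member of staff did the act. A field for which seller acted is a useful addition.
- In SAP 2.2.1, define the three secondary outcomes as acts by any staff member in the store during the visit.
- Put the same rule in the collector manual.

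The cost is a few lines of text, with no extra visits.

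**If visits are complete**, which the Protocol's reference to a manuscript and its 2024 access dates suggest is possible:

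- State the rule buyers actually used, from the manual and the training record.
- If the literal rule was followed, label the three outcomes as acts by the main seller, and say that store-level rates may be higher.
- Use the free-text notes at Question 41 only as a partial sensitivity check. They have no coding rule, and Question 41 is skipped whenever Question 23 is Yes.
- Add a sensitivity table over assumed *m*, *s_u* and *s_c*, including the equal and reversed cases.

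This costs a short analysis and a sentence of reporting.
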